### 9.2.8 Study Follow-up

Women will be followed from enrollment through the end of their pregnancy and infants will be followed through 1 year after birth. Specific data to be collected during different periods during the follow-up are detailed below. Safety reporting will be ongoing throughout the duration of the study.

---

### **During Follow-up of Pregnancy (estimated at 14, 21 and 34 weeks gestation)**

- Date of contact
- Reporter of information (eg, patient, PCP, OB, neurologist [indication specialist], nurse midwife, other)
- Current weight
- Changes in lifestyle risk factors (eg, smoking, caffeine consumption, alcohol use, illicit drug use)
- Number of migraines since last follow-up; frequency and duration, with or without aura, number of migraines requiring treatment, any prescription migraine treatments, and days of acute migraine treatments each month (by trimester)
- Changes in comorbid conditions
- Erenumab-aooe treatment (including start and stop dates, dose, dosing frequency, reason for discontinuation [if applicable])
- Current medications, including start and stop dates (eg, any other OTC migraine treatment(s), folic acid and other vitamins, herbal remedies or supplements, vaccinations, or other medications used to treat chronic conditions or comorbidities)
- Pregnancy status, if applicable:
  - Gestational age at contact
  - Any prenatal testing performed and results (eg, rubella titer, toxoplasmosis, venereal disease research laboratory test, hepatitis screen, ultrasounds, amniocentesis, maternal serum alpha-fetoprotein screen, glucose screen)
  - Pregnancy outcome (eg, live births, spontaneous abortions, stillbirths, elective or therapeutic terminations, reason for elective or therapeutic termination [eg, prenatal testing finding, risk to mother's health, undesired pregnancy], and autopsy results and pathology reports, if available)
  - Congenital malformations noted (including description and attribution)
- Patient AEs and SAEs (including event, start date, ongoing or end date, seriousness, severity, relationship to erenumab-aooe, outcome, action taken)

### **At Delivery (estimated within 4 weeks of delivery date)**

- Reporter of information (eg, patient, PCP, OB, neurologist [indication specialist], nurse midwife, infant HCP, other)
- Pregnancy outcome (eg, live birth, stillbirth, spontaneous abortion, elective or therapeutic termination)
- Reason for elective or therapeutic termination (eg, prenatal testing finding, risk to mother's health, undesired pregnancy), if applicable
- Autopsy results and pathology reports, if available
- Mode of birth (vaginal delivery, assisted delivery/cesarean section, type of anesthesia)
- Number of migraines since last follow-up; number of migraines requiring treatment, and any prescription migraine treatments
- Changes in comorbid conditions

- Erenumab-aooe treatment (including start and stop dates, dose, dosing frequency, reason for discontinuation [if applicable])
- Current medications, including start and stop dates (eg, any other OTC migraine treatment(s), folic acid and other vitamins, herbal remedies or supplements, vaccinations, or other medications used to treat chronic conditions or comorbidities)
- Changes in lifestyle risk factors (eg, smoking, caffeine consumption, alcohol use, illicit drug use)
- Patient AEs and SAEs (including event, start date, ongoing or end date, seriousness, severity, relationship to erenumab-aooe, outcome, action taken)
- Infant characteristics:
  - Gestational age at birth
  - Sex
  - Birth weight
  - Length
  - Head circumference
  - Birth order (for multiple births), and number of fetuses
  - Apgar scores (1, 5, and 10 minutes)
  - Congenital malformations noted (including description and attribution)
  - Vaccination information
  - Whether infant is breastfed
  - Infant medication(s)
  - Infant AEs and SAEs (including event, start date, ongoing or end date, seriousness, severity, relationship to erenumab-aooe, outcome, action taken)

**Infant Follow-up (estimated at 12, 26 and 52 weeks of age)**

- Reporter of information (eg, patient, PCP, OB, neurologist [indication specialist], nurse midwife, infant HCP, other)
- Feeding behavior (including breastfeeding)
- Weight
- Length
- Head circumference
- Postnatal growth and development (ie, social/emotional, language/communication, neurocognitive, movement/physical development milestones)
- Breastfeeding status
- Evidence of any new congenital malformations and growth alterations since last follow-up
- Vaccination information
- Patient and infant AEs and SAEs (including event, start date, ongoing or end date, seriousness, severity, relationship to erenumab-aooe, outcome, action taken)

### Early termination of study participation contact, if applicable:

- Reporter of information (eg, patient, PCP, OB, neurologist [indication specialist], nurse midwife, other)
- Assessments appropriate for the time of withdrawal
  - Pregnancy status (eg, gestational age at contact, any prenatal testing performed and results)
  - Pregnancy outcome (eg, live births, spontaneous abortions, stillbirths, elective or therapeutic terminations, reason for elective or therapeutic termination [eg, prenatal testing finding, risk to mother's health, undesired pregnancy], mode of birth, and autopsy results and pathology reports, if available)
  - Infant characteristics (eg, postnatal growth and development, feeding behavior, weight, length, head circumference, breastfeeding status, vaccine information, current medications)
  - Evidence of any new congenital malformations and growth alterations since the last follow-up
  - Patient and infant AEs and SAEs (including event, start date, ongoing or end date, seriousness, severity, relationship to erenumab-aooe, outcome, action taken)
- Termination status
  - Completion of follow-up
  - Early termination/withdrawal (including date of withdrawal, reason for withdrawal)
- Erenumab-aooe treatment, current medications, pregnancy status, and infant characteristics (for live births), and safety events will be collected similarly as during study follow-up.

### 9.3 Variables

The reporter of variable information can be the patient, patient's HCP, or infant's HCP where applicable (see [Section 9.2.6](#)). [Appendix F](#) provides a summary table of data collection elements.

#### 9.3.1 Exposure Assessment

The following criteria will be used to assign women to 1 of 2 cohorts, as determined by exposure to erenumab-aooe:

- **Erenumab-aooe Exposed Cohort:** Documentation of exposure to erenumab-aooe from 16 weeks prior (to allow for the half-life of erenumab-aooe) to LMP or at any point during the patient's pregnancy. Exposure information recorded will include start and stop dates, dose, dosing frequency, reason for discontinuation (if applicable).
- **Internal Comparator Cohort:** Documentation of no exposure to any CGRP mAb from 5 half-lives prior to LMP or at any point during the patient's pregnancy. Note: exposure assessments will not be determined for the external comparator cohort(s), as patient-level data is not available; these cohort(s) represent the prevalence of birth defects in the general population.

### 9.3.2 Outcome Assessment

As shown in [Table 3](#), all outcomes defined in this section will be assessed in both the erenumab-aooe exposed and internal comparator cohorts, as patient-level data will be collected prospectively. The outcome of major congenital malformations will be compared to the prevalence reported for the external comparator population that provides aggregate data, only (MACDP).

**Table 3. Summary Key Outcome Assessments Across Data Sources**

	Erenumab-aooe Exposed	Internal Comparator	MACDP a
Primary Outcome			
Major congenital malformations	X	X	X
Secondary Outcomes			
Pregnancy complications: preeclampsia, pregnancy-induced hypertension, preterm labor, gestational diabetes, placenta previa	X	X	
Pregnancy outcomes: elective or spontaneous termination, fetal death, preterm birth	X	X	
Infant outcomes: minor congenital malformations, size for gestational age, low birth weight, postnatal growth and development	X	X	

MACDP = Metropolitan Atlanta Congenital Defects Program

a Additional external comparator data sources may be used (see [Section 9.2.1.1](#)), but similar to MACDP, only aggregate data will be available for comparison to this registry.

#### 9.3.2.1 Primary Outcome

##### 9.3.2.1.1 Major Congenital Malformations

Congenital malformations will be classified according to the MACDP classification system ([MACDP, 2016](#)) (see [Section 9.2.1.1.1](#)) and adjudicated major congenital malformations will serve as the primary outcome in this study (minor malformations will be excluded from the primary analysis). The MACDP classification lists major and minor birth defects that are tracked by MACDP, as well as conditions that are never included and those that are included only under certain circumstances. The code is based on the International Classification of Diseases, 9th Revision, Clinical Modification and the British Pediatric Association Classification of Diseases.

All potential major congenital malformations identified by the patient's HCP or the infant's HCP will be evaluated by a qualified, independent committee of at least

3 teratologists using all available medical records (see [Section 9.8.4](#)). The classification of potential major congenital malformations will be based upon the teratologists' adjudication, who will be blinded to patient exposure status. The adjudication process will involve the classification of congenital anomalies by both MACDP and EUROCAT classification systems. In the event any European data sources become available for descriptive comparison to this registry, the EUROCAT classification would be implemented to ensure comparability. However, this is not currently planned.

### **9.3.2.2 Secondary Outcomes**

#### **9.3.2.2.1 Pregnancy Complications**

##### **9.3.2.2.1.1 Preeclampsia**

Primary preeclampsia will be based on HCP reported diagnosis. It is often defined as the presence of hypertension on 2 occasions at least 4 hours apart after 20 weeks gestation (in a woman with a previously normal blood pressure) and proteinuria; or in the absence of proteinuria, a new-onset hypertension accompanied by 1 of the following conditions: thrombocytopenia, renal insufficiency, impaired liver function, pulmonary edema, or cerebral or visual symptoms ([ACOG, 2019](#)).

##### **9.3.2.2.1.2 Pregnancy-Induced Hypertension**

High blood pressure (elevated: systolic between 120-129 and diastolic less than 80 mg Hg; Stage 1 hypertension: systolic between 130–139 or diastolic between 80–89 mm Hg; Stage 2 hypertension: systolic at least 140 or diastolic at least 90 mm Hg) associated with pregnancy, as diagnosed by the treating HCP ([ACOG, 2019](#)).

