Data will be collected from patients and their HCPs during pregnancy and through 1 year after birth (infant's HCP and/or the patient). Where the HCP is unavailable, the patient can report the necessary information to the study coordinating center (CC) staff for entry into the electronic case report form (eCRF). If information is reported by both the patient and the HCP, the HCP reported data will take precedent.

Follow-up will cease if the patient is lost to follow-up, consent is withdrawn, death (mother and/or infant), study termination, or the study ends (whichever comes first).

- Variables

- Outcome Variables

- Primary Outcome:

- Major congenital malformations classified according to the Metropolitan Atlanta Congenital Defects Program (MACDP) classification system (see [Section 9.2.1.1.1](#)). All potential congenital malformations identified by the patient's HCP or the infant's HCP will be evaluated by a committee of at least 3 qualified, independent teratologists, who will be blinded to patient exposure status, using all available medical records.

- Secondary Outcomes:

- Pregnancy Complications

- Pre-eclampsia, as diagnosed by the treating HCP; often defined as the presence of hypertension on 2 occasions at least 4 hours apart after 20 weeks gestation (in a woman with a previously normal blood pressure) and proteinuria; or new-onset hypertension accompanied by thrombocytopenia, renal insufficiency, impaired liver function, pulmonary edema, or cerebral or visual symptoms.
          - Pregnancy-induced hypertension: high blood pressure associated with pregnancy as diagnosed by the treating HCP.
          - Preterm Labor: as diagnosed by the treating HCP; defined by regular contractions of the uterus resulting in changes in the cervix that start before 37 weeks of pregnancy.

- Gestational Diabetes: as diagnosed by the treating HCP; characterized by carbohydrate intolerance with first onset or first recognition during pregnancy; or have a record of a failed oral glucose tolerance test during pregnancy.
- Placenta Previa: as diagnosed by the treating HCP; the patient's cervix is fully or partially covered by baby's placenta.
- Pregnancy Outcomes
  - Elective or Therapeutic Pregnancy Terminations: defined as any induced or voluntary fetal loss during pregnancy.
  - Spontaneous Abortions: defined as loss of a fetus due to natural causes at < 20 weeks of gestation.

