##### **9.3.2.2.1.4 Gestational Diabetes**

Gestational diabetes will be based on HCP reported diagnosis. It is often characterized by the development of carbohydrate intolerance with first onset or first recognition during pregnancy; a record of an oral glucose tolerance test during pregnancy will also be accepted for data collection, where available ([ACOG, 2018](#)).

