##### **9.3.2.2.2.5 Preterm Birth**

A live birth will be classified as preterm prior to 37 weeks of gestation ([www.cdc.gov](http://www.cdc.gov)). Preterm birth will be categorized as early preterm (< 34 weeks), late preterm (34 weeks to 36 weeks), and early term (37 weeks to 38 weeks).

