#### 9.7.2.4 Analysis of the Primary and Secondary Endpoints

The prevalence of major and minor congenital malformations will be calculated using MACDP convention. Major malformations will be analyzed separately from minor malformations, with the primary analysis including only adjudicated major congenital malformations. The total prevalence will be calculated by dividing the number of adjudicated cases of each event (observed in live births, fetal deaths, elective or therapeutic terminations, and at any gestational age) by the total number of pregnancies (excluding spontaneous terminations and ectopic or molar pregnancies). The prevalence at birth will be calculated as number of cases observed in live births and stillbirths divided by the total number of births (stillbirths + live births). Data analysis for major congenital malformations will be based on first trimester exposure to erenumab-aooe.

The prevalence of pregnancy complications, including preeclampsia, pregnancy-induced hypertension, gestational diabetes, placenta previa, and preterm labor, will be summarized by dividing the number of each event by the total number of pregnant women.

The prevalence of spontaneous abortions will be calculated by dividing the number of fetal losses occurring before 20 weeks gestation by the total number of pregnancies.

The prevalence of elective and therapeutic abortion will be estimated similarly as separate outcomes.

Prevalence of preterm birth will be calculated by dividing the number of cases by the total number of births (stillbirths + live births). The prevalence of small-for-gestational-age will be calculated by dividing the number of cases by the total number of live births.

For growth and developmental delays, the prevalence will be calculated as the number of cases divided by the total number of live births.

Prevalence of primary and secondary outcome measures will be presented with 95% CIs for binomial proportion. The analyses summarized in this section will be performed on the erenumab-aooe exposed cohort and the internal comparator cohort consisting of pregnant women with migraine who were not exposed to erenumab-aooe; Characteristics can be matched or stratified in relation to the exposed cohort to control for important covariates such as maternal age (see [Section 9.7.2.5.1](#)).

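### Three secondary outcomes are worded inconsistently, so that non-cases could be counted as pregnancy-induced hypertension, gestational diabetes or preterm birth, and the preterm proportion is slightly understated

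*Protocol*

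**What the plan says.** **Pregnancy-induced hypertension.** Section 9.3.2.2.1.2 opens with "High blood pressure (elevated: systolic between 120-129 and diastolic less than 80 mg Hg; Stage 1 hypertension: systolic between 130–139 or diastolic between 80–89 mm", adds a Stage 2 band, and closes with "associated with pregnancy, as diagnosed by the treating HCP". It gives no gestational age at onset and does not ask for normal pressure beforehand. The preeclampsia text just above it (9.3.2.2.1.1) mentions both: "after 20 weeks gestation (in a woman with a previously normal blood pressure". The abstract (Section 4) defines pregnancy-induced hypertension by the provider's diagnosis, with no bands. Section 9.3.4 says that pregnancy complications rely on a reported diagnosis and not on individual readings, and uses blood pressure as its example.

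**Gestational diabetes.** Section 9.3.2.2.1.4 bases the outcome on the provider's diagnosis, then adds that "a record of an oral glucose tolerance test during pregnancy will also be accepted for data collection". The abstract's alternative criterion is that the woman "have a record of a failed oral glucose tolerance test during pregnancy".

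**Preterm birth.** Section 9.3.2.2.2.5 defines it as a live birth before 37 weeks. The next sentence reads "Preterm birth will be categorized as early preterm (< 34 weeks), late preterm (34 weeks to 36 weeks), and early term (37 weeks to 38". The abstract calls the same bands optional additional stratifications. On the denominator, Section 9.7.2.4 says: "Prevalence of preterm birth will be calculated by dividing the number of cases by the total number of births (stillbirths + live births". The sentence after that divides small-for-gestational-age by live births alone.

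**The concern.** Section 8.2 lists maternal, fetal and infant outcomes for comparison with the internal comparator, and Section 9.7.2.5.1 makes that comparison by risk ratio. The teratologist committee adjudicates malformations. Complications rest on what is reported, and under Section 9.4.2 the patient answers the provider's questionnaire when the provider does not respond. The written definitions are therefore the main protection against miscounting.

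Each inconsistency leaves a different opening:

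- A coordinator or programmer working from 9.3.2.2.1.2 alone could record a woman with a reading of 120 to 129, or one who was hypertensive before conception, as an event. Any difference in chronic hypertension between the cohorts would then enter an outcome meant to reflect the pregnancy.
- Working from 9.3.2.2.1.4 alone, a normal glucose tolerance test could be taken as support for a case.
- A table built from 9.3.2.2.2.5 would put births at 37 to 38 weeks under a preterm heading.
- The preterm proportion uses a denominator that includes births which cannot enter its numerator.

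In a safety registry, non-cases counted at a similar rate in both cohorts pull a risk ratio towards 1.

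**Working it through.** The protocol gives no prevalence or power figure for these outcomes, so there is no stated number to reproduce. Most of the check sets the text side by side.

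**1. Hypertension.** Section 9.3.2.2.1.1 says the outcome is the reported diagnosis and then describes what that diagnosis often means. Section 9.3.2.2.1.2 has no such hedge: the bands qualify the term high blood pressure directly. The lowest one, "elevated: systolic between 120-129 and diastolic less than 80 mg Hg", is set apart from the two bands labelled hypertension. If Section 9.3.4 governs, the bands have no function. If the bands govern, Section 9.3.4 is wrong. The two need reconciling.

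Could the registry separate the cases? Appendix F Table 1 records high blood pressure as a medical condition, with diagnosis and start date. It places current pregnancy-induced hypertension in the same category. Table 2 records new conditions with start dates. The data to separate prior from new disease exist, but no stated rule uses them. Appendix F has no blood pressure field, so a numeric threshold could not be applied.

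**2. Gestational diabetes.** The abstract asks for a failed test and the outcome section asks only for a record. Glucose test results are collected (Section 9.2.8; Appendix F Tables 1 and 2), so a failed result can be identified.

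**3. Preterm categories.** The bands below 34 weeks and 34 to 36 weeks together make up births before 37 weeks. The band of 37 to 38 weeks lies wholly outside the definition.

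**4. Preterm denominator.** Let s be stillbirths divided by all births (live plus still). Then

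preterm live births / all births = (preterm live births / live births) × (1 − s).

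Section 9.2.1.1.1 gives s as 7.6 and 8.0 per 1,000.

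- s = 0.0076: factor 0.9924.
- s = 0.0080: factor 0.9920. A true 10.00% (assumed) would be reported as 9.92%.
- With 749 live births, all births = 749 / 0.992 = 755.0, so about 6 units are added to the denominator.
- If stillbirth were 16 per 1,000 in the exposed and 8 per 1,000 in the comparator (assumed), the preterm risk ratio would be multiplied by 0.984 / 0.992 = 0.992.

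**5. What miscounting could do (assumed inputs only).** Suppose a fraction f of non-cases is counted in both cohorts, the true comparator risk is p, and the true risk ratio is 2.0. The observed risks are p + (1 − p)f and 2p + (1 − 2p)f. For p = 6% and f = 5% they are 10.7% and 16.4%, a ratio of 1.53.

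| Assumed p | f = 5% | f = 10% | f = 20% |
|---|---|---|---|
| 3% | 1.36 | 1.21 | 1.11 |
| 6% | 1.53 | 1.35 | 1.19 |
| 10% | 1.66 | 1.47 | 1.29 |

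Neither p nor f is in the protocol. The table shows direction and sensitivity, not an estimate.

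**The case against.** A reader might infer that these outcomes are defined so that non-cases count: hypertension from 120 mm Hg, gestational diabetes from any test, preterm birth up to 38 weeks. The documents do not support that.

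- **Hypertension.** Section 9.3.4 excludes readings as the basis, and 9.3.2.2.1.2 itself ends on the provider's diagnosis. A reading of 120 does not by itself make a case. The contrast with preeclampsia is also weaker than it looks, because the onset and prior-pressure wording there describes how the condition is often defined and is not a strict criterion.
- **Gestational diabetes.** The provider's diagnosis comes first. Accepting a test record for data collection is ambiguous, and it does not say that a normal test is a case.
- **Preterm birth.** The definition stops before 37 weeks, and the extra band is labelled term. The categories exceed the preterm total only if a band labelled term is counted as preterm.
- **Denominator.** It adds no non-cases, and its effect is negligible at plausible stillbirth rates.

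All of this stands. It reduces the point from a wrong case definition to conflicting text. It does not remove the conflicts: the bands still contradict Section 9.3.4, the failed-test condition is still missing from the outcome section, early term is still listed under preterm birth, and numerator and denominator still differ. A statistical analysis plan might add counting rules, but these statements already stand in the protocol and disagree with one another.

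**Conclusion.** The concern holds as one of inconsistent wording in three secondary outcomes. Non-cases could be counted; the text does not require it. The one effect that can be sized is the preterm denominator, an understatement of about 0.8% of the proportion at the protocol's own stillbirth figures of 7.6 to 8.0 per 1,000. That is a tidy-up.

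The size of any hypertension or gestational diabetes misclassification cannot be computed from the document. Statements that a risk ratio of 2.0 would shrink to a particular value rest entirely on assumed false-positive rates, and Section 9.3.4 argues against rates that come from blood pressure readings. The primary outcome, major congenital malformations, and the sample size of 1421 women for 749 live births do not depend on any of this. The corrections are still worth making, because they are specific and nearly free.

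**What to change.** 1. **Section 9.3.2.2.1.2:** remove the blood pressure bands, or state that they do not define a case. Keep the provider's diagnosis as the basis, in line with Section 9.3.4 and the abstract. Add a rule that uses the collected diagnosis start dates and the baseline history of high blood pressure, so that hypertension predating the pregnancy is a baseline covariate and not an event. Do not add a numeric threshold, because Appendix F collects no blood pressure values.
2. **Section 9.3.2.2.1.4:** reconcile with the abstract by restoring the condition that the glucose tolerance test was failed.
3. **Section 9.3.2.2.2.5:** report early term (37 to 38 weeks) as a separate, non-preterm stratum.
4. **Section 9.7.2.4:** divide preterm live births by live births, as is already done for small-for-gestational-age.

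The cost is protocol wording and matching table shells. Start dates, prior conditions, glucose test results and gestational age are already collected. The one consequence to expect is that there may be somewhat fewer hypertension events, because pre-existing disease is no longer eligible to be counted.
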